4.3 Determination of Sample Size

The study plans to enroll up to 54 participants in total, including up to 30 in Part 1A, 18 in Part 1B, and 6 in Part 2. The exact number of participants cannot be determined precisely in advance but depends upon occurrence of DLTs and potential need for expanded cohorts.

The sample size in Part 1A is based on a 1+3 design with 3 planned cohorts (12 participants) and 3+3 design for 3 cohorts (18 participants). The sample size in Part 1B is based on a 3+3 design with 3 planned cohorts (18 participants). Part 2 of the study may enroll up to 6 participants based on a 3+3 design with 1 cohort.

The number of participants is not based on statistical power calculations. No inferential statistics will be calculated. The sample size is considered sufficient to evaluate the primary objective of this study.

4.4 Analysis Populations

All participants who receive at least one dose of either study drug will be included in the safety population. This population will be used to summarize safety data. This population will also be used to summarize baseline data and for PK, PD, and immunogenicity analyses.

4.5 Demographics and Baseline Characteristics

Participant disposition, demographics, baseline characteristics, disease history, and medical history will be summarized using descriptive statistics.

4.6 Study Drug Exposure and Concomitant Medications

Study drug exposure, ART, and concomitant medications will be summarized by descriptive statistics. The summary of study drug exposure will include descriptive statistics as well as frequency counts for the number of doses or cycles received, the total dose actually administered as well as the total dose intended, and the dose intensity which is calculated as percentage of total dose actually administered divided by total dose intended during study treatment period.

Duration of study treatment (months) will be calculated as:

- (date decided to discontinue treatment date of first dose + 1)/(365.25/12) for participants who have discontinued treatment.
- (date of data cutoff date of first dose + 1)/(365.25/12) for participants whose treatment is ongoing.

The summary of concomitant medications will include the number and percentage of participants who receive any concomitant medications as well as each concomitant medication by drug class. Concomitant medications are coded using the World Health Organization Drug Dictionary.

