4.1.3 Part 2: Multi-Dose Expansion Cohort: Fixed-Dose of MGD020 and Fixed-Dose of MGD014

Part 2 commences only after an MTD or MAD of MGD020 in combination with MGD014 has been determined in Part 1B. Part 2 is a multi-dose expansion cohort with sequential infusions of a fixed dose of MGD020 in combination with a fixed dose of MGD014 administered Q2W for 3 combination doses over 4 weeks (**Table 3**). MGD020 is dosed at the MTD/MAD determined in Part 1B (i.e., MTD_{1B}/MAD_{1B}). MGD014 is dosed at 300 mcg/kg, as determined from Study CP-MGD014-01.

Up to 6 participants may be enrolled in Part 2 using a conventional 3+3 design. If 2 or more participants in the cohort of 6 participants experience a DLT, enrollment and further dosing of ongoing participants will be suspended pending further assessment of safety data.

Table 3 MGD020 and MGD014 Combination Multi-Dose Expansion Cohort Scheme (Part 2)

Cohort	MGD020 ^a (mcg/kg)	MGD014 (mcg/kg)	Design
1	MGD020 MTD _{1B} /MAD _{1B}	300	3+3

- a The MGD020 dose is determined by the combination MTD or MAD in Part 1B.

Participants who completed Part 1 may be considered for enrollment in Part 2, provided they meet all eligibility criteria, did not experience DLT in Part 1, and do not have detectable ADA against MGD014 and/or MGD020 at the completion of Part 1.

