4.4 Guidelines for Dose Modification

No dose modifications are allowed. A reduction of the infusion rate is allowed during re-challenge for an infusion reaction ([Section 7.1](#)).

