4.4.1 Dose Delays

Hold study drug administration for toxicity, pending assessment, management, and resolution of the AE. If the AE is assessed as unrelated to study drug(s) or does not meet DLT criteria, study drug(s) may be restarted at the previous dose and schedule, after appropriate recovery.

In Part 2, a dose delay of up to 7 days is allowed for drug-related or non-drug related AEs. Refer to [Section 7.1](#) for specific guidance on restarting study therapy after infusion reactions. A dose delay $>$ 7 days due to drug-related toxicity will prompt study drug discontinuation.

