14.4 Study Drug Exposure and Concomitant Medications

Study drug exposure and concomitant medications will be summarized by descriptive statistics. The summary of study drug exposure will include descriptive statistics as well as frequency counts for the number of doses received, the total dose actually administered as well as the total dose intended, and the dose intensity which is calculated as percentage of total dose actually administered divided by total dose intended during whole treatment period.

Concomitant medications are coded using the World Health Organization Drug Dictionary.

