- e On dosing visits (Day 1, 15, and 29), vital signs are measured pre-infusion; at 15 and 30 min after start of infusion (± 5 min); at end of infusion (EOI) of all study drug(s) (± 5 min); at 15, 30, 45, and 60 min post-infusion of last study drug (± 5 min); then every 60 min (± 10 min) until 6 hours after EOI or until the end of the monitoring period (see [Section 6.5.1](#)), whichever comes first (until 2 hours after EOI on Day 15 and 29). During non-dosing in-person visits, vital signs are assessed once.
- f ECGs are performed in triplicate (approximately 1 min apart). At screening and EOSV, ECGs will be taken at one time point. On dosing visits (Day 1, 15, and 29), ECG is recorded pre-infusion, at EOI of all study drug(s), at 30 and 60 min after EOI of last study drug, and as clinically indicated. ECGs after EOI have ± 10 min window.
- g Assess participants for adverse events. Participants are also instructed to contact the study coordinator or investigator if any signs or symptoms of an AE occur at any time during the study.
- h Optional leukapheresis is performed only after the participant is enrolled in the study. If the participant consents to this optional procedure, a baseline leukapheresis is completed. If a baseline leukapheresis was performed, a second leukapheresis procedure is completed 2 weeks (+2 week window) following the final study drug infusion.
- i Additional and/or more frequent safety laboratory tests may be performed as clinically indicated per the investigator's discretion.
- j Clinical laboratory assessments scheduled for Day 1 can be obtained within 7 days prior to infusion. See [Section 9.11](#) for detailed list of assessments. Indirect bilirubin is required if participant on atazanavir.
- k Day 43 hematology is assessed only for participants undergoing leukapheresis. This hematology assessment is performed within the window for the scheduled leukapheresis.

- 1 Participants of childbearing potential only. Serum pregnancy test is required at screening. Subsequent pregnancy tests may use serum or urine. Results must be reviewed before study drug infusion on Day 1, Day 15, and Day 29. If screening test is performed within 72 hours of first infusion, repeat testing on Day 1 may be deferred.
 - m Reflex HCV PCR viral load test is performed only if positive for HCV antibody.

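### SAP 4.6 ends treatment duration at the decision to discontinue, not the last infusion, so time on hold counts as treatment and a Part 2 participant stopped after two doses can show longer treatment than a completer

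*SAP*

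**What the plan says.** SAP 4.6 gives two formulas for treatment duration in months. The first is "date decided to discontinue treatment date of first dose + 1)/(365.25/12) for participants who have discontinued treatment". The second is "date of data cutoff date of first dose + 1)/(365.25/12) for participants whose treatment is ongoing". Both should be read with a minus sign between the two dates; its absence from the extracted text is not treated as an error. Neither formula uses the date of the last infusion. Protocol 14.4, which also covers exposure, has no duration formula, so the SAP is the only source.

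Dosing is by infusion. Parts 1A and 1B give a single dose. Protocol 4.1.3 has the Part 2 combination "administered Q2W for 3 combination doses over 4 weeks", and the footnotes to the Part 2 schedule in Protocol Appendix 1 fix the days: "On dosing visits (Day 1, 15, and 29), vital signs are measured pre-infusion".

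Protocol 4.4.1 has study drug held while a toxicity is assessed and resolves. In Part 2 it allows a delay of up to 7 days, and a delay of more than "7 days due to drug-related toxicity will prompt study drug discontinuation". Protocol 4.5 lists completion of planned dosing among the conditions that end study drug, but neither document says which date then serves as the decision date.

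SAP 4.6 also reports the number of doses received, total dose given, total dose intended, and dose intensity, defined as "percentage of total dose actually administered divided by total dose intended during study treatment period". Protocol 14.4 has "total dose actually administered divided by total dose intended during whole treatment period". Neither period is defined.

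**The concern.** The date of a decision is an administrative date. With discrete infusions, a participant whose next dose is on hold receives nothing while the hold lasts, yet the SAP formula keeps counting until someone decides to stop. The protocol's own delay rule can put that decision more than a week after a dose that was due and never given. Someone who received two of three doses can then appear to have been treated for longer than someone who received all three.

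For completers the formula has no defined input. They fall under the discontinued branch only if completion is read as a discontinuation, as Protocol 4.5 allows, and the end date is then whatever is entered. This affects nearly everyone in Parts 1A and 1B, planned at up to 30 + 18 = 48 of 54 participants.

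Safety and tolerability is the primary objective, and the exposure table is the context in which the adverse event tables are read. A duration row that lengthens because a dose was withheld is a poor description of exposure.

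**Working it through.** **Inputs.** Month length in SAP 4.6: 365.25/12 = 30.4375 days. Part 2 infusions: Days 1, 15 and 29 (Protocol Appendix 1). Longest permitted delay: 7 days (Protocol 4.4.1). Part 2 size: up to 6 (Protocol 4.1.3).

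**The plan's own figure.** (29 − 1)/7 = 4.0 weeks from first to third infusion, which agrees with the stated four weeks. The SAP states no duration in months.

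**Formula.** Months = (end day − first dose day + 1)/30.4375. With first dose on Day 1, this is end day/30.4375.

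**Completer.** The end date is undefined, so it has to be assumed.
- Day 29 (third infusion on schedule): 29/30.4375 = 0.95
- Day 36 (third infusion delayed by the full 7 days): 36/30.4375 = 1.18
- Day 43 (if the end date were recorded at the Day 43 visit): 43/30.4375 = 1.41

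**Participant stopped after two doses (Days 1 and 15), by decision day.**

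| Decision day | Months under SAP 4.6 | Longer than a Day 29 completer (0.95)? |
|---|---|---|
| 15 | 0.49 | No |
| 20 | 0.66 | No |
| 28 | 0.92 | No |
| 29 | 0.95 | Equal |
| 30 | 0.99 | Yes |
| 37 | 1.22 | Yes |
| 43 | 1.41 | Yes |

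Day 37 is the first day on which a dose due on Day 29 is more than 7 days late (29 + 7 + 1). The ratio to the Day 29 completer is 37/29 = 1.28. The ratio to the stopper's own first-to-last-infusion span is 37/15 = 2.47.

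**Effect on the cohort summary.** Take five completers ending on Day 29 and one stopper decided on Day 37.
- SAP rule: (5 × 29 + 37)/6 = 30.3 days, or 1.00 months.
- Last-infusion rule: (5 × 29 + 15)/6 = 26.7 days, or 0.88 months.
- All six completing: 29 days, or 0.95 months.

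Losing a dose moves the mean up under the SAP rule and down under the last-infusion rule.

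**Check of the remedy.** With the last infusion as end date, the two-dose stopper has 15/30.4375 = 0.49 months. If dose 2 had itself been late (Day 22 or 23), the figure is 0.72 to 0.76. The earliest completer (Day 28, using the 1-day visit window) has 0.92. The order holds throughout.

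**Single-dose parts.** If the end date is the dosing day, every participant has 1/30.4375 = 0.03 months, a constant.

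**Dose intensity in the same case.** By Day 37 all three doses had fallen due, so two of three given is 2/3 = 67%, whether the denominator is the full regimen or the doses due by the decision.

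**The case against.** The case against giving this much weight is substantial, and most of it stands.

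- **The reversal is conditional.** It needs a decision on Day 30 or later. A dose-limiting toxicity is itself a listed reason to stop (Protocol 4.5), and a decision on Days 15 to 28 gives 0.49 to 0.92 months, shorter than the completer.
- **The delay route is narrow.** Under Protocol 4.3 almost any related event of Grade 2 or above is dose-limiting, and the two exceptions (brief Grade 2 laboratory abnormalities and brief Grade 2 fatigue) both end within 7 days. The rule on delays beyond 7 days therefore mainly reaches persistent Grade 1 related events, or slow assessment.
- **The comparison depends on an assumed end date for completers.** If it were recorded at Day 43, the completer would show 1.41 months and the Day 37 stopper would not exceed it. SAP section 5 leaves programming specifications to a separate plan, which may settle this. It remains true that the SAP formula as written does not.
- **Dose counts are reported alongside.** The same SAP paragraph requires them, so two doses against three would be visible.
- **First-to-last-infusion span is a convention too.** Protocol 2.3.2.1 gives a half-life of 10 to 12.5 days for MGD014, so drug persists after the last infusion. That is fair, but a decision date does not measure persistence either.

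A reader might also infer that dose intensity would hide the missed dose by showing 100%. The documents do not support this for the delayed-dose cases: it is 67% for the Day 37 decision. For one dose with a Day 23 decision it is 50% even if the denominator stops at the participant's own decision, because dose 2 had fallen due by then. A value of 100% after an early stop would need both that truncated denominator and a decision before the next due date, and then no duration reversal arises. Nothing in either document says that the intended dose is truncated.

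**Conclusion.** The point holds in limited form. SAP 4.6 states a formula that counts hold time as treatment and leaves the end date undefined for completers. In Part 2 it can show a two-dose stopper at 1.22 months against 0.95 for an on-schedule completer, when the stopper's infusions span 0.49 months. This rests on three assumptions: dose 3 due on Day 29, a decision on Day 37, and a completer end date of Day 29. Below Day 30 there is no reversal, though any decision after the last infusion still adds days without dosing.

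A reader might go further and conclude that the tolerability message for Part 2 is reversed. The documents do not support that. The primary endpoint in Protocol 3.1 is the incidence of treatment-emergent adverse events, serious adverse events and adverse events leading to discontinuation. SAP 4.8.1 tabulates numbers and percentages of participants, including those withdrawn from study drug, and specifies no exposure-adjusted rates. No escalation or suspension rule uses duration. The effect is one misleading row in a descriptive exposure table, for a cohort of at most 6. It is a small correction, but one participant is enough to move that row the wrong way.

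**What to change.** In SAP 4.6, replace both duration formulas with one for Part 2: date of last infusion − date of first infusion + 1, in days, applied alike to completers and early stoppers. State that the last infusion means the last of either study drug. In Parts 1A and 1B the quantity is constant and can be omitted.

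As an optional clarification, define the dose-intensity denominator as the full protocol-planned dose, separately for each drug: one dose in Part 1A (MGD020 only) and Part 1B, three in Part 2. Protocol 4.4 says "No dose modifications are allowed", so missed or incomplete infusions are the main way to fall short. MGD020 is infused first, and Protocol 7.1.3 bars further study drug at a visit after a Grade 3 infusion reaction, so the amounts received of the two drugs can differ. The same wording would remove the difference between the SAP and Protocol 14.4 over the undefined treatment period.

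The cost is one derivation line for duration, a second if the denominator is clarified, and the matching SAP text. No new data are needed, and no dosing or discontinuation rule changes.

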4.7 Protocol Deviations

Major protocol deviations will be identified prior to database lock for final analysis and will be listed and summarized.

4.8 Safety Endpoints and Analyses

4.8.1 Adverse Events

Treatment-emergent adverse events (AEs) will be summarized in tables and listings. All AEs prior to treatment (e.g., due to study-related procedure) will be presented in listings only. Tables will display the number and percent of participants that experience the given event.

AEs will be coded to the Medical Dictionary for Regulatory Activities (MedDRA). Events will be summarized by system organ class, preferred term, relationship to study drug, and highest severity.

The following tables of AE data will be created to summarize the number and percent of participants who experience at least one event of each of the following types:

- All AEs
- Study drug-related AEs
- Study drug-related AEs by severity grade

- AEs by severity grade
- All severe AEs (SAEs) (this may be a listing if there are few events)
- Study drug-related SAEs
- Fatal AEs (this may be a listing if there are few events)
- AEs that result in study discontinuation
- AEs that lead to withdrawal of study drug
- AEs with severity grade 3 or greater
- Study drug-related AEs with severity grade 3 or greater

All of these tables will display the number and percent of participants that experience the given event and will display events by System Organ Class (SOC) and Preferred Term (PT). Events will be displayed alphabetically for SOC and in descending order of overall PT incidence within each SOC.

4.8.2 Laboratory Values and Analyses

Summaries of laboratory values will display descriptive statistics for numerically quantified labs. Summaries will be grouped by lab panel (e.g., hematology, blood chemistry, and urinalysis) and will be displayed by visit for each lab parameter.

In cases where an abnormality resulted in a repeat lab test, the repeat value will be used for the summaries. A list of repeated labs including original values and repeat values will be included.

Shift tables will be used to display the number and percent of participants who have a shift in their lab value normality between baseline and each post-baseline visit.

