12.2 Adverse Event Collection and Documentation

12.2.1 Adverse Events

AEs and SAEs will be collected from the time the participant consents to study participation. AEs and SAEs reported between the time the participant signs the informed consent form and administration of the first dose of study drug will be captured as concurrent medical history unless the events are attributed to protocol-specified procedures.

Events attributed to protocol-specified procedures will be collected on the AE eCRFs and SAE Report Form, as appropriate.

AEs, regardless of seriousness, severity, or relationship to study drug(s), are documented in the source and the eCRF, including:

- Duration, severity, and seriousness of each AE.
- Action taken with respect to the study drug(s).
- Investigator's attribution/causality assessment.

- Any medications used to treat the AE.
- Outcome of the event.

A diagnosis should be recorded when signs and symptoms are due to a common etiology (e.g., cough, runny nose, sneezing, sore throat, and head congestion should be reported as "upper respiratory infection"). All treatment measures for AE management will be recorded. All non-serious AEs should be entered into the eCRFs within 10 days of study site awareness.

Clinical Laboratory Changes: Clinical laboratory test results are evaluated by the investigator for clinical significance. The investigator is responsible for reviewing the results of all laboratory tests in a timely manner. The investigator may repeat the laboratory test or request additional tests to verify the results of laboratory tests.

Clinically significant laboratory abnormalities are reported as AEs. A laboratory abnormality is considered clinically significant if it is associated with study drug discontinuation, study drug dose reduction or delay, requires an intervention, or it is suggestive of disease or organ toxicity.

Laboratory abnormalities associated with a diagnosed AE are not reported as separate AEs. For example, report renal failure or hematuria, not the laboratory abnormality (e.g., elevated creatinine or urine red blood cells increased).

The sponsor reports all suspected unexpected serious adverse reactions (SUSARs) to the regulatory authorities and the investigator. The investigator must report SUSARs to the IRB of record as required by the site's institutional policy.

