4 STATISTICAL METHODOLOGY

4.1 General Considerations

The majority of the statistical summaries for this Phase 1 study will be descriptive. Summary statistics will consist of absolute and relative frequencies of each category of discrete variables of means, standard deviations, coefficient of variations, medians, and minimum and maximum values of continuous variables.

All data summaries and tabulations will be conducted using SAS® software Version 9.4 or higher.

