4.2 Missing Data

Data that are reported as missing will be treated as missing in all data summaries. Imputation rules for partially recorded dates, in case that the complete dates are required to perform an analysis, will be provided in the Statistical Programming Plan (SPP). In descriptive summaries for safety, observations that are spurious (extreme relative to the majority of the data) will not be altered or removed from the summary.

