5 LIST OF TABLES, LISTINGS, AND FIGURES

The list of tables, listings, and figures (TLFs) and associated shells planned for the CSR based on the analyses described in this SAP will be provided in a separate SPP, which will also include data reporting conventions and programming specifications for the development of these TLFs. Note that the SPP will not include TLF shells for the exploratory analyses described in Sections 4.12.2-4.12.7 as they will be performed and reported separately.

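### SAP 4.8.2 replaces an abnormal laboratory value with its repeat even when the original is valid, so what enters the by-visit summaries depends on the result

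*SAP*

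**What the plan says.** SAP 4.8.2 plans descriptive statistics for numeric laboratory results by panel, parameter and visit. It then sets the replacement rule: "In cases where an abnormality resulted in a repeat lab test, the repeat value will be used for the summaries". The original is kept in one place: "A list of repeated labs including original values and repeat values will be included". The section also plans a table that classifies results: "Shift tables will be used to display the number and percent of participants who have a shift in their lab value normality", from baseline to each post-baseline visit. It does not say whether the shift tables take the original or the repeat.

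SAP 4.1 defines the numeric summaries as "means, standard deviations, coefficient of variations, medians, and minimum and maximum values of continuous variables". SAP 4.2 says that in safety summaries "observations that are spurious (extreme relative to the majority of the data) will not be altered or removed from the summary".

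Protocol 12.2.1 describes when repeats arise: "The investigator may repeat the laboratory test or request additional tests to verify the results of laboratory tests". It also says: "Clinically significant laboratory abnormalities are reported as AEs". Protocol 14.7.2 plans laboratory summaries by visit and contains no replacement rule. SAP 5 defers "data reporting conventions and programming specifications for the development of these TLFs" to a separate programming plan, which is not among the documents.

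**The concern.** A rule that replaces a value only when that value is abnormal selects on the outcome. Replacing a result from a bad specimen is sound. Replacing a valid result because it was abnormal and someone rechecked it is different: the tables then describe a mixture of scheduled draws and selected later draws.

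The case that matters is a real but short-lived change. The protocol foresees such changes: Protocol 4.3 makes an exception for a Grade 2 laboratory abnormality that resolves within 72 hours without clinical complications. Protocol 12.2.1 requires adverse event reporting only for abnormalities judged clinically significant. A valid transient abnormality could therefore be neither a DLT nor an adverse event, and SAP 4.8.2 would also take it out of the tables. SAP 4.8.2 sets no limit on how late the repeat may be.

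Scheduled values are few. As the schedules in Protocol Appendix 1 read, chemistry after Day 1 is due on Days 2, 8, 22 and 43 in Parts 1A and 1B, and on Days 15, 29 and 78 in Part 2. One replacement changes one of four or one of three values for that participant and analyte.

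**Working it through.** The documents give no figure to reproduce. The rate of abnormal values, the share repeated and the agreement between original and repeat are all absent, so everything numeric below is assumed.

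**Step 1: what the rule can do.** Take one analyte at one visit. If the original is normal, it stays. If it is abnormal and not repeated, it stays. If it is abnormal and repeated, the repeat is used, and that may be normal or abnormal. Abnormal can become normal; normal cannot become abnormal. This needs replacement analyte by analyte. If a whole panel were replaced, another analyte could turn abnormal; the SAP does not say.

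**Step 2: numeric summaries, no drug effect.** Assume original and repeat are standard normal with correlation r, limits at ±1.96, and a fraction f = 0.5 of abnormal values repeated.
- Mean: unchanged, by symmetry.
- Variance after the rule = 1 − f(1 − r²) × 2 × 1.96 × φ(1.96), where φ(1.96) = 0.0584, so the last product is 0.229.
- r = 0.5: 1 − 0.5 × 0.75 × 0.229 = 0.914, SD 0.956.
- r = 0.9: 1 − 0.5 × 0.19 × 0.229 = 0.978, SD 0.989.

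The SD is thus about 1% to 4% smaller.

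**Step 3: numeric summaries, real transient rise.** Assume the scheduled draw is raised by 1 SD and the rise has gone by the repeat. The upper limit is 1.96 and f = 0.5.
- Loss in the visit mean = f × [P(Z > 0.96) + (1 − r)φ(0.96)], with P = 0.1685 and φ(0.96) = 0.2516.
- r = 0.5: 0.5 × (0.1685 + 0.1258) = 0.147, so 1.00 is shown as about 0.85.
- r = 0.9: 0.5 × (0.1685 + 0.0252) = 0.097, so 1.00 is shown as about 0.90.
- Values above the limit: 16.9% of scheduled draws, against 9.2% (r = 0.5) to 9.7% (r = 0.9) after the rule.

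**Step 4: shift tables, if they follow the rule.** Use the model of Step 2, where 5% of scheduled draws are abnormal. Let k be the probability that a repeat of an abnormal value is again abnormal: 0.185 at r = 0.5 and 0.593 at r = 0.9. Without the rule, normal-to-abnormal shifts are 5% × (1 − k), or 4.07% and 2.04%. With the rule, by simulation:

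| Abnormal values repeated | r = 0.5 | r = 0.9 |
|---|---|---|
| Half at baseline, half post-baseline | 2.53% | 1.64% |
| All at baseline, none post-baseline | about 4.7% | 2.75% |

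The direction therefore depends on where the repeats fall.

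**Step 5: repeats that worsen.** With no drug effect, a repeat of an abnormal value is more extreme than the original in about 9% (r = 0.5) to 30% (r = 0.9) of cases. A single minimum or maximum can therefore move either way.

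**The case against.** The strongest reply is that using a verified result is defensible. With no drug effect, suppose all variation within a pair is noise. The underlying abnormal rate in the Step 4 model is then 2 × [1 − Φ(1.96/√r)]: 0.56% at r = 0.5 and 3.88% at r = 0.9. With half repeated, the rule shows 5% × (1 − 0.5 + 0.5k), that is 2.96% and 3.98%, closer to the underlying rate than the scheduled 5%. This stands. A reader might infer that the rule understates a true abnormality rate, and the documents do not support that. The harm needs a real change that has faded by the repeat, and they do not show how often that would happen.

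A reader might also infer that the by-visit summaries will show fewer abnormal values. Those summaries are means, SDs, medians and ranges, and they do not count abnormal values. Only the shift tables do, and SAP 4.8.2 does not tie them to the rule. Nor would they necessarily show fewer shifts, as Step 4 demonstrates. Heavier repeating at baseline is an assumption but a plausible one: laboratory limits govern entry (Protocol 5.1), and Day 1 results must be reviewed before dosing (Protocol 9.11.1).

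SAP 4.2 might be read as contradicting the rule. It pulls the other way, but it concerns outliers in general and 4.8.2 is a specific rule for repeats, so the point does not rest on it.

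Finally, the unseen programming plan may define a repeat, set a time limit or settle the shift tables. Nothing in the documents shows that it overrides the stated rule.

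**Conclusion.** The concern holds as a minor one. SAP 4.8.2 makes replacement depend on the result and not on the validity of the original. That is certain from the text. The consequence is small without a drug effect and moderate within the affected tables if a real transient change is rechecked after recovery. Both statements rest on assumed normal models, original-repeat correlations of 0.5 to 0.9 and half of abnormal values repeated. Shift tables, if they follow the rule, are distorted in a direction that cannot be fixed in advance.

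The inference that safety conclusions or dose decisions are compromised is not supported. The primary endpoint is adverse events (Protocol 3.1). DLTs (Protocol 4.3) are defined on treatment-related adverse events, and escalation (Protocol 4.2 and 14.9) rests on review of safety data; neither uses these tables. Originals and repeats are listed, and with cohorts of 1 to 6 participants the listing can be read in full.

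**What to change.** In SAP 4.8.2, state that the original scheduled value is used in the by-visit summaries and in the shift tables, at baseline and post-baseline, unless the specimen or result is documented as invalid; only then use the repeat. Keep the listing of originals and repeats.

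A shift table from baseline to the worst valid post-baseline value, including repeats and unscheduled tests, is optional. It would capture repeats that worsen. If added, it should be labeled as expected to show more noise-driven shifts than the by-visit tables. In the no-effect model, worst-of-three-visits shifts run at 4.4% (r = 0.9) to 10.6% (r = 0.5), against 2.0% to 4.1% per visit.

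The cost is a change of SAP wording and minor programming. The documents do not show whether specimen invalidity is recorded; if it is not, a flag is needed. The downside is slightly higher and noisier tabulated abnormality rates. In the 5% example with half repeated, the difference is about 1 to 2 percentage points (5% against 3.98% to 2.96%).
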